Secondary objectives are

1. to assess the degree of acceptance of the procedure and
2. to evaluate the efficacy of the technique according to the age of the patients and, therefore, their suggestibility.

PATIENTS AND METHODS

Design

1:1 parallel group unicenter randomized clinical trial.

Randomisation and masking

Randomisation will be carried out in blocks, depending on the day of the operation (day with hypnosedation or day with distraction), without the dermatologists or the anaesthetist performing the operation having prior knowledge of either the assigned day or the "suggestibility" of the cases, respectively.

The blinding will be achieved by assigning different investigators to each phase of the study, with one designated as responsible for recruitment ([name]), another for intervention and control ([name]), and another for subsequent evaluation in the post-anaesthesia recovery unit (URPA) and at 24 hours (responsible nursing staff).

Participants

Children scheduled for dermatological surgery will be recruited for major outpatient surgery (MOS) at the National Paraplegic Centre.

The following inclusion criteria are established:

1. age between 5 and 16
2. any gender / sex

3. A class I or II of anaesthetic risk according to the American Society of Anesthesiologists,
4. to be in a percentile between P3 and P97 in weight and height,
5. without known drug allergies, and
6. having fasted 6 hours for solids and 2 hours for water.

The following exclusion criteria have been established:

1. mental retardation
2. attention deficit,
3. behavioural disorders,
4. previous treatment with hypnosis,
5. history of neurological pathology or psychomotor retardation,
6. previous pain-related pathology,
7. obstructive sleep apnoea syndrome (OSAS)

Recruitment will be carried out by the principal investigator from the surgical waiting list for a period of 5 months.

All patients who meet the inclusion criteria will be given informed consent and an information sheet, both on the anaesthetic procedure and on hypnosis as an adjuvant technique.

Intervention, control and procedures

Patients will be randomly distributed to one of the following groups:

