Waking up will be carried out in the operating theatre with subsequent transfer to the Post-Anaesthesia Care Unit (PACU), where, in addition to control of constants, pain will be assessed using adapted scales (see variables and measurements below), and analgesics will be administered where necessary (if VAS>4 paracetamol will be used, 15 mg/kg, and if pain persisted, magnesium metamizole at a dose of 20 mg/kg).

Evaluation and Outcome Measures

The following outcome variables are established:

- Main variable: Total dose of propofol and additional need for opioids during the operation, measured in mg/kg of weight as recorded intra-operatively.
- Impact on pain and analgesic needs, both in the immediate post-operative period and 24 hours after the operation, measured by pain scales adapted to age and cognitive maturation (Visual Analogical Scale (VAS) from 10 years and Face Drawing Scale or FPS-r from 5 to 9 years), need for paracetamol, ibuprofen or other analgesics. The scales are given to the children by the nurse in charge at the PACU, who will be also responsible for the 24-hour post-surgery follow-up, and did not know the group to which each patient belonged. The analgesic need will be collected from the medical logs.
- Degree of satisfaction with the procedure, using a scale of 1 to 10, administered at the time of discharge from hospital to the children or their guardians.

Statistical analysis

For the descriptive analysis, central tendency and dispersion measures will be used (median and 25th to 75th percentiles, P₂₅₋₇₅) for quantitative variables, and absolute and relative frequencies for qualitative ones. The comparison of the outcome measures between the intervention group and the control group will be carried out by means of non-parametric tests: chi-square and Fisher's exact test for qualitative outcome measures, and Mann-Whitney's U for the quantitative ones.

An age-based subgroup analysis will be conducted (under 7 years and over).

The significance level will be set at a value of $p < 0.05$ and the analysis will be carried out with Excel®.

A sample of 30 patients will be calculated to detect a 40 mg dose difference between the two groups, with a risk α of 0.05 and a risk β of 0.20 in a bilateral contrast and assuming a common standard deviation of 33.3 and a loss to follow-up rate of 10%.

Ethical aspects

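### Age is known for every child but plays no part in the main propofol comparison, which is unadjusted and has no planned estimate or interval

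*Protocol*

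**What the plan says.** The main variable is "Total dose of propofol and additional need for opioids during the operation, measured in mg/kg of weight" (protocol, Evaluation and Outcome Measures). The Statistical analysis section, which the SAP repeats, assigns quantitative outcomes to "Mann-Whitney's U for the quantitative ones". Neither document plans a covariate, a stratified test, an estimated difference or a confidence interval.

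Eligibility is "age between 5 and 16" (Participants). Randomisation is in blocks by operating day, with no stratification by age (Randomisation and masking). In the analysis, age appears once: "An age-based subgroup analysis will be conducted (under 7 years and over". A secondary objective is to look at the technique's efficacy by age.

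The trial is sized "to detect a 40 mg dose difference between the two groups", which is said to need 30 patients. The other inputs are a two-sided α of 0.05, power of 0.80, an SD of 33.3 and 10% losses.

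**The concern.** No sentence lists age as a baseline variable. It must nevertheless be available for every child, because it decides eligibility, the choice of pain scale and the subgroup. It is fixed before allocation, so adjusting for it cannot bring in post-allocation bias.

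The trial is small, the age range is wide, and nothing in the design balances age between arms. If age predicts propofol dose, an unadjusted test leaves that variation as noise. In a trial where the arms happen to differ in age, the result also cannot be separated from that difference. An adjustment chosen after an imbalance has been seen would look data-driven, so the choice belongs in the SAP.

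Separately, a trial sized on a 40 mg difference that plans a p-value but no estimate cannot say how its result compares with that target.

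**Working it through.** **Inputs from the documents.** Total 30, 1:1; difference 40 mg; SD 33.3 (unit not stated, taken as mg); two-sided α 0.05; power 0.80; 10% loss; ages 5-16.

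**Inputs assumed.** Ages spread evenly over 5-16; an age-dose correlation r between 0 and 0.5; individual randomisation.

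**1. The plan's own figure.** The normal formula gives 2 × (1.96 + 0.84)² × (33.3/40)² = 10.9, so 11 per arm. The t-based calculation gives 12 per arm, and 12/0.9 = 13.3, so 14 per arm (28 in total). Allowing for the 0.955 efficiency of Mann-Whitney under normality, 12/0.955 = 12.6, so 13 per arm; 13/0.9 = 14.4, so 15 per arm. That is 30 in total, as stated. The calculations in steps 4 and 5 use 13 evaluable children per arm, except where 15 is stated.

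**2. Chance gap in mean age, 15 per arm.**
- SD of whole-year ages 5 to 16 = 3.45 years.
- SE of the gap = 3.45 × √(2/15) = 1.26 years.
- Typical (mean absolute) gap = 1.26 × √(2/π) = 1.0 year.
- 95% limit = 1.96 × 1.26 = 2.47 years.

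**3. What the gap moves.** Shift = (gap/3.45) × r × 33.3.

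| Gap | r = 0.3 | r = 0.5 |
|---|---|---|
| 1.0 year (typical) | 2.9 mg | 4.8 mg |
| 2.47 years (95% limit) | 7.1 mg | 11.9 mg |

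The typical shift is therefore about 7-12% of the 40 mg target (2.9/40 and 4.8/40).

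**4. False positives under no effect (simulated).** Over all randomisations Mann-Whitney rejects in about 4.5% of trials. The arms differ by more than 2 years in 14% of trials at 13 per arm and 11% at 15 per arm. Within those trials Mann-Whitney rejects in about 7% (r = 0.3) or 11-13% (r = 0.5). A linear model with age rejects in about 5%.

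**5. Power at 13 per arm (simulated).** The normal case uses the plan's 40 mg and SD 33.3. The skewed case assumes a dose of 2.5 mg/kg plus a lognormal extra amount (log SD 0.9), with the extra reduced by a factor e in one arm. No child has a zero dose.

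| Scenario | r | Mann-Whitney | Rank-based, age-adjusted |
|---|---|---|---|
| Normal | 0 | 79% | 80% |
| Normal | 0.5 | 79% | 89% |
| Skewed | 0 | 73% | 74% |
| Skewed | 0.5 | 74% | 84% |

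Across the rank-based options, the gain is none to about 1-2 points for r up to 0.2, about 4 points at r = 0.3 and about 6-10 points at r = 0.5. A stratified Wilcoxon test can lose up to about 3 points if age does not predict dose.

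A linear model on the raw dose behaves differently. In the normal case it has 82%, 86% and 91% power at r = 0, 0.3 and 0.5. In the skewed case it has only 58-68%, against 73-74% for Mann-Whitney.

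**6. Scale.** The sample size is in mg and the outcome in mg/kg. In mg, the protocol's initial dose of 2.5 mg/kg alone ties dose to weight: 16 kg × 2.5 mg/kg = 40 mg, the whole target difference. Dividing by weight removes at least part of that link. A correlation assumed on one scale therefore does not carry over to the other, and the mg shifts in step 3 are illustrations.

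**The case against.** The strongest reply is that the planned test is sound and the benefit is hypothetical. Much of this stands. Under individual randomisation Mann-Whitney keeps its overall error rate and has about 80% power on the plan's own inputs. Chance imbalance is already covered by that error rate. No correlation between age and dose is given. The secondary objective treats age as changing the effect of the technique through suggestibility, which is not the same as predicting dose. At r = 0.2 or below there is almost nothing to gain.

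The reply is also right about one possible remedy. The protocol has a fixed initial dose plus additional amounts and allows inhalational induction, so a floor, a right tail and some zero doses are possible. A rank test suits such data, and replacing it by a linear model on the raw dose could lose power. With 10% zero doses (assumed), Mann-Whitney had 50-53% power and the linear model 25-30%.

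What does not stand is the inference that age should therefore be left out. Continuous-age adjustment on ranks matched or slightly exceeded Mann-Whitney in every scenario in the power table, including r = 0. The age subgroup is no substitute: it looks at the effect within age bands and does not adjust the main comparison.

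**Conclusion.** The point holds as a worthwhile, inexpensive improvement. The main comparison leaves out a baseline variable that the trial already has, and plans no estimate or interval. The gain in power runs from none to about 10 points for r between 0 and 0.5, and the documents cannot say where in that range the trial lies. It rests on even ages, individual randomisation, 13 evaluable children per arm and no zero doses.

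A reader might infer more, and the documents do not support it:
- **That the test is biased or invalid.** It is neither under individual randomisation. The loss is in precision and in protection within the trials that happen to be imbalanced.
- **That a gap of 2.5 years, and a shift of 7-12 mg, is to be expected.** That is the 95% limit; the typical gap is about 1 year.
- **That age adjustment deals with whole days sharing an arm.** It does not. Allocation by day leaves fewer independent units and could make age imbalance larger than shown here. The p-value has to reflect it separately.

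**What to change.** In the SAP, and in the matching protocol section:

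1. Make the main analysis of propofol (mg/kg) a rank-based comparison adjusted for age: either rank ANCOVA with continuous age, or a Wilcoxon test stratified by age group. Name one in advance.
2. Take the p-value by re-randomising operating days in the way they were actually allocated. The number of days is not stated. If it is small, there are few possible allocations and power will be below the figures above.
3. Report an estimated difference with its 95% confidence interval, for example Hodges-Lehmann or an age-adjusted mean difference.
4. Keep the unadjusted Mann-Whitney test and a linear model with age as sensitivity analyses.
5. Reconcile the unit of the sample-size difference and SD (mg) with that of the outcome (mg/kg).

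The cost is a few lines of SAP text, a statistical package in place of Excel, one degree of freedom, and up to about 3 points of power for the stratified version if age turns out not to predict dose. No new data are needed.

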**Effectiveness of hypnoanalgesia for dermatological surgery in
children: Randomised clinical trial**

NCT CHT00028

Document Date: March 15, 2019

Statistical plan

For the descriptive analysis, central tendency and dispersion measures will be used (median and 25th to 75th percentiles, P_{25-75}) for quantitative variables, and absolute and relative frequencies for qualitative ones.

The comparison of the outcome measures between the intervention group and the control group will be carried out by means of non-parametric tests: chi-square and Fisher's exact test for qualitative outcome measures, and Mann-Whitney's U for the quantitative ones.

An age-based subgroup analysis will be conducted (under 7 years and over).

The significance level will be set at a value of $p < 0.05$ and the analysis will be carried out with Excel®.

A sample of 30 patients was calculated to detect a 40 mg dose difference between the two groups, with a risk α of 0.05 and a risk β of 0.20 in a bilateral contrast and assuming a common standard deviation of 33.3 and a loss to follow-up rate of 10%.
